Cognitive Training: Subjects are randomly assigned to either active or sham training. Subjects are blinded to assignment. Both groups complete 8 total sessions of training over one month; each session take approximately 30 minutes.

Follow-up Assessment: Subjects complete follow-up Psychiatric and Neuroimaging Assessments. These assessments are identical to the corresponding Baseline Assessments and are designed to assess behavioral and neural response to training.

E2 Due to COVID-19, participants may be contacted via phone and e-mail to participate in some follow-up surveys. Once contacted, we may set up a zoom meeting. A member of the research team will explain that this is completely optional and will review the online survey process with the family over the phone or zoom. If the family agrees to participate, the research team member will e-mail a RedCap survey link that will start with the consent form. Researcher will walk participant through how to complete the surveys over the phone or zoom. Participants will have adequate time to review the consent document and there will be an e-mail address provided if the participant should have any questions. The participants e-signature through REdCap will have a time stamp. After the consent is signed, research staff will send an electronic copy of the signed consent document to the participant via e-mail. Subject Selection and Withdrawal

Subjects will be screened over the phone standardized parent-report psychiatric instruments (Screen for Anxiety and Related Disorders, SCARED; and Mood and Feelings Questionnaire, MFQ).

2.a Inclusion Criteria

We will recruit children between the ages of 7-17 for this study with current separation anxiety disorder, generalized anxiety disorder, and/or social phobia.

2.a Exclusion Criteria

Exclusion criteria include prior diagnoses of ADHD, autism spectrum disorder, intellectual disability (IQ<70), a significant medical problem, or current use of psychotropic medication other than SSRIs (children who are currently taking an SSRI and are still experiencing symptoms of anxiety will not be exluded).

2.b Ethical Considerations

There are no major ethical concerns associated with this study.

2.c Subject Recruitment Plans and Consent Process

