either the center of the screen or the periphery. The child will also view different shapes and faces (happy, sad, angry, scared, and neutral) while engaged in the computer game. Following the game, the child will answer questionnaires (general questionnaire, SCARED, Childhood Depression Inventory (CDI), MFQ, and Pubertal Development Scale(PDS)) and participate in the child version of the K-SADS and PARS.

F3 Visit 2

Neuroimaging Visit:

MRI Simulation/Stillness Training: Child participants will complete a MRI training session to collect data on movement inhibition and prepare subjects for future MRI testing. Research indicates that an MRI simulation exercise prior to scanning increases the likelihood of a successful scan. Given that, an introduction to/explanation of the scanning procedure and a simulation exercise will be introduced at the conclusion of the child assessment. The child interviewer will engage the child in an MRI simulation. In this simulation, the child will practice lying still in a mock scanner environment. The child will practice lying still while listening to recorded MRI sounds and receiving visual feedback of their head movement. Feedback will be provided using motion tracking software, MoTrak 3D, connected to a video screen viewed from the scanner by the research subject. Subject movement and responsiveness to the training procedures will be recorded. Children will also be shown a video in which the scanning center is introduced and the scanning procedure is explained to the child. In the video, the child will see another child participating in the MRI procedure.

The NEUROIMAGING TRAINING could take place on the same day following the IN-PERSON ASSESSMENT, on the same day before the NEUROIMAGING VISIT, or on its own day, depending on the preference of the participant.

Before the MRI scan, parents will complete the MRI Safety checklist to ensure the child safety in the scanner and the child will complete a shortened version. The child will complete a 90 minute MRI scan before and after the cognitive training. We acquire a T1-weighted MP-RAGE, a T2 image, 4 five-minute "resting" functional scans, and 4 four-minute "task" functional scans. During the resting scans, the subjects with fixate a cross and during task blocks, subjects will complete the attention tasks. There will be no contrast used for this MRI scan.

F4 Visit 3-10

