The child will participate in 8 thirty minute training sessions, twice a week for four weeks. They will complete the cognitive training program that has been designed by [name].

On the day of sessions 2, 4, 6, and 8 subjects and parents complete the SCARED either in office or by a secure e-mail survey invitation via REDcap in order to assess anxiety over treatment. After session 8, subjects will be asked to rate tolerability of the training on a 5 point Likert scale.

F5 Visit 11

This visit will be after all 8 training sessions are completed and is identical to visit 1.

F6 Visit 12

This visit will be after all 8 training sessions and visit 11 are completed and is identical to visit 2.

Follow-up via Phone/Zoom

A member of the research team will explain that this is completely optional and will review the online survey process with the family over the phone or zoom. If the family agrees to participate, the research team member will e-mail a RedCap survey link that will start with the consent form. Researcher will walk participant through how to complete the surveys over the phone or zoom. Participants will have adequate time to review the consent document and there will be an e-mail address provided if the participant should have any questions. The participants e-signature through REdCap will have a time stamp. After the consent is signed, research staff will send an electronic copy of the signed consent document to the participant via e-mail.

G Statistical Plan

G1 Sample Size Determination and Power

Power analyses for two-tailed, two independent groups (active versus sham) comparisons were performed using G*Power 3.1. Based on prior work, we expect training to have a minimum effect size of 0.3 for changing symptoms of anxiety. Based on this effect size, we have 83% power to detect group differences in treatment effects (n=90, plus 10% failure). Power calculations are not computed for fMRI analyses because we have no effect size estimate; sample size is similar to other recent pilot studies.

G2 Interim Monitoring and Early Stopping

Subjects may withdraw from the study at any time. Each cognitive training session takes place in the lab. Study staff will converse with study subjects before and after each training session in order to assess for any adverse events.

G3 Analysis Plan / Statistical Methods

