The primary outcome will be reduction in symptoms of anxiety as measured by the SCARED in study Phase 2. Total SCARED scores at sessions 2, 4, 6, and 8 will be subtracted from the baseline SCARED score, yielding a delta SCARED score for each

visit. These data will be analyzed with a mixed random effects repeated-measures model. In this model, time, treatment (active versus sham), and time x treatment interaction are fixed effects; baseline SCARED scores and subject within treatment are random effects; and delta SCARED scores are the dependent variable. Our hypothesis predicts a significant time x treatment interaction, with a greater decrease in anxiety from pre- to post- training in the active relative to the sham group. Secondary outcomes will include symptoms of anxiety on the PARS and diagnostic status.

We will test whether active versus sham training significantly reduces symptoms in children with anxiety disorders. The primary outcome will be reduction in symptoms of anxiety as measured by the PARS. We will perform a 2 x 2 ANOVA with treatment arm (active versus sham) and time (pre- versus post-training) as effects of interest.

G4 Missing Outcome Data

We will use an intention-to-treat analysis and carry the last observation forward. Because this is a pilot study, we will also compare active versus sham treatment among completers in a follow-up analysis.

G5 Unblinding Procedures

The principal investigator will be made aware of each subject's assignment after that subject has completed all study procedures including post-treatment psychiatric assessment.

H Data Handling and Record Keeping

H1 Confidentiality and Security

Telephone conversations about the study, the consent process, and all portions of the study will take place in a private office. All subjects will be marked with a random identification number so names will not be recorded on any of the data. All data will be stored in locked filing cabinets and on password protected computers. Also, only the research team will have access to study information. Participants can refuse to answer any questions and withdraw from the study at any time.

H2 Training

All current study staff have extensive experience in study procedures, based on similar prior studies performed in the lab. Any new personnel will be trained by current study staff.

H3 Case Report Forms and Source Documents

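### The PARS arm-by-time ANOVA is in effect a change-score test; adjusting post-training PARS for baseline PARS costs about 1% of variance at worst and may gain precision from data already collected

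*Combined protocol and SAP*

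**What the plan says.** Section G3 (Analysis Plan / Statistical Methods) gives PARS one analysis sentence: "We will perform a 2 x 2 ANOVA with treatment arm (active versus sham) and time (pre- versus post-training) as effects of interest". The sentence before it makes PARS the endpoint: "The primary outcome will be reduction in symptoms of anxiety as measured by the PARS". Nothing in G3 names baseline PARS as a covariate, names the arm-by-time interaction as the PARS test, or specifies a within-child error term for PARS. An interaction hypothesis does appear in G3, but in the SCARED paragraph.

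Both PARS values are available. At Visit 1 (F2) parents complete the PARS interview and children "participate in the child version of the K-SADS and PARS". For Visit 11, F5 says: "This visit will be after all 8 training sessions are completed and is identical to visit 1".

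Two other provisions bear on the size of the effect. G4 says: "We will use an intention-to-treat analysis and carry the last observation forward". G1 says: "we have 83% power to detect group differences in treatment effects (n=90, plus 10% failure".

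The only baseline term in G3 belongs to the separate SCARED model, where "baseline SCARED scores and subject within treatment are random effects".

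**The concern.** A change score fixes the slope of post-training PARS on baseline PARS at 1. Adjustment estimates that slope from the data. When the true slope is below 1, as it is with equal SDs and any correlation below 1, the change score carries baseline noise into the treatment comparison that could be removed at no collection cost.

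In a pilot of 90 children, the stake is the width of the confidence interval for the treatment effect on an outcome that C1 and part of G3 call primary.

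The wording leaves a second, smaller opening. The sentence lists arm and time as the effects of interest. The arm main effect averages the pre and post values, so under randomization it estimates only half the post-training difference. It is not the test that the hypothesis needs.

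**Working it through.** **Inputs from the documents.** 90 children randomized 50/50, so 45 per arm (Study Timetable; 2.d); two-sided testing (G1); PARS at Visits 1 and 11 (F2, F5); LOCF (G4); 10% failure allowance (G1).

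**Assumed, because the documents do not give them.** Alpha 0.05; the pre-post correlation rho; the ratio SDpost/SDpre.

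**The plan's own figure.** G1's 83% power is not reproduced on its stated basis. A standardized difference of 0.3, two-sided, at 45 per arm gives 29%. Reading 0.3 as Cohen's f (d = 0.6) gives 80% at N = 90 and 84% at N = 99. Nothing below depends on the 83%.

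**Step 1: equivalence.** With two time points per child, the repeated-measures interaction F equals the squared two-sample t on change. In a test dataset both were 5.8019.

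**Step 2: variances.** Set the post SD to 1 and the pre SD to s = 1/(SDpost/SDpre).

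- Change: Vc = 1 + s² - 2·rho·s
- Adjusted: Va = 1 - rho²
- Difference: Vc - Va = (s - rho)², never negative

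Estimating the slope multiplies Va by (N - 3)/(N - 4) = 87/86 = 1.012. That 1.2% is the expected worst case, reached when the true slope is exactly 1.

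**Step 3: extra children the change-score analysis needs**, Vc/(1.012·Va) - 1.

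Examples at rho = 0.5:

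- Equal SDs: Vc = 1 + 1 - 1 = 1.00 and Va = 0.75; 1.00/(0.75 × 87/86) = 1.318, or 32%. Then 90 adjusted children carry the information of about 90 × 1.318 = 119 analysed by change.
- Ratio 1.25 (s = 0.8): Vc = 1 + 0.64 - 0.80 = 0.84; 0.84/0.7587 = 1.107, or 11%.

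| SDpost/SDpre | rho 0.3 | 0.5 | 0.7 | 0.8 |
|---|---|---|---|---|
| 0.8 | 97% | 73% | 57% | 54% |
| 1 | 52% | 32% | 16% | 10% |
| 1.25 | 26% | 11% | 1% | -1% |
| 1.43 | 16% | 4% | -1% | 2% |

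**Step 4: LOCF.** PARS has only one earlier value, so a missing post-training PARS becomes the baseline value. Suppose a random 10% are carried forward and the rest fall by 0.5 SD (both assumed). With f = 0.10 and m = 0.5:

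- Change variance = (1-f)Vc + f(1-f)m²
- Post variance = (1-f) + f·s² + f(1-f)m²
- Covariance = (1-f)·rho·s + f·s²

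Net of the slope cost, the gains become 43, 27, 14, 8% (equal SDs) and 22, 9, 1, -1% (ratio 1.25), in the same order of rho.

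**Step 5: 95% CI half-width**, t·√(2V/45), in post-score SD units, at rho 0.3, 0.5, 0.7, 0.8. Degrees of freedom are 88 (change) and 87 (adjusted).

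- Change, equal SDs: 0.496, 0.419, 0.325, 0.265
- Change, ratio 1.25: 0.451, 0.384, 0.302, 0.251
- Adjusted, both cases: 0.402, 0.365, 0.301, 0.253

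**Step 6: power**, change to adjusted, at 45 per arm. G1 does not say what 0.3 is measured in, so three readings are shown.

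| Reading of 0.3 | SDs | rho 0.5 | rho 0.7 |
|---|---|---|---|
| d, in post-score SDs | equal | 29% to 37% | 44% to 50% |
| d, in post-score SDs | ratio 1.25 | 34% to 37% | 50% to 50% |
| d, in change-score SDs | equal | 29% to 37% | 29% to 33% |
| f (d = 0.6), in change-score SDs | equal | 80% to 90% | 80% to 86% |

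**Step 7: no within-child error term.** If the four cells were treated as independent groups, the interaction variance would be overstated by 1/(1 - rho) with equal SDs. At rho = 0.5 the critical value 1.97 acts as 1.97/√0.5 = 2.79, so the actual type I error is about 0.5% instead of 5%. That reading would be conservative and would waste power.

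**The case against.** The strongest reply is that nothing here is an error. A two-by-two arm-by-time ANOVA is a conventional analysis of one pre and one post value, and the change-score test is unbiased with correct type I error. That stands: this is an efficiency recommendation.

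The gain also cannot be established from the documents. It ranges from large to slightly negative, depending on a correlation and SDs that are nowhere stated. That stands too. Entry requires children "with current separation anxiety disorder, generalized anxiety disorder, and/or social phobia", which could compress baseline spread and push the SD ratio above 1, where the gain shrinks. But no PARS threshold is stated, so this is conjecture in either direction.

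The 1% bound is an expectation. In a single dataset with a chance baseline imbalance of 2 standard errors and a true slope of 1, the cost would be about 4/88 = 4.5% of variance. This qualifies the bound without changing the balance.

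The interaction can fairly be inferred from the hypothesis in the SCARED paragraph. That is the natural reading, and the equivalence in Step 1 relies on it, but the PARS sentence does not say it.

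Finally, G3 calls PARS both secondary and primary. If it is secondary, less hangs on the choice, though the arithmetic is the same.

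**Conclusion.** The point holds as a recommended improvement. For any SDs and correlation, the adjusted analysis has an expected variance at most about 1.2% above that of the change-score test at 45 per arm. The direction is certain apart from that cost; the size is not. With equal SDs, the change-score analysis needs 10% to 52% more children over correlations from 0.8 down to 0.3, or 8% to 43% under the LOCF assumptions above. With a post-to-pre SD ratio of 1.25 or more and a correlation of 0.7 or above, the gain is close to nil.

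Adjustment does not rescue the trial's power: if 0.3 is a standardized difference in post-score SD units, power reaches only 37% at a correlation of 0.5 and 50% at 0.7.

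No precision loss is claimed for the SCARED analysis, which already carries a baseline term.

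**What to change.** Replace the ANOVA sentence in G3 with:

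> Post-training PARS will be regressed on treatment arm and baseline PARS; the arm coefficient will be reported with a 95% CI.

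If the ANOVA is kept, name the repeated-measures arm-by-time interaction as the test.

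The cost is one sentence, one degree of freedom and about 1% of variance, with no new data. Because G5 discloses each child's assignment to the principal investigator once that child has finished, record when the change was decided and that it was made without sight of outcome data by arm.

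Optionally, for clarity only, state that baseline SCARED enters its model as a fixed covariate with subject as the random effect. Whether SCARED or PARS is primary is a separate contradiction in G3 and needs its own decision.

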Computer-based cognitive training programs provide a safe, tolerable tool to reduce VAN reactivity and potentially treat pediatric anxiety disorders. Randomized controlled trials already support the use of cognitive training programs with targets different from the VAN. 20-22 For example, attention bias modification (ABM) trains individuals to ignore threatening stimuli in order to improve symptoms of anxiety. While promising, this treatment generates no more than modest effects on symptoms. The treatment in this study was specifically designed to reduce reactivity of the overactive VAN associated with pediatric anxiety disorders, by training individuals to actively ignore salient stimuli while maintaining attention on a particular task. By targeting a particular brain network that implements a core psychological process disrupted early in the developmental pathway to anxiety disorders, this novel treatment could represent a major improvement to current cognitive training approaches and may have a more substantial impact on symptoms.

B2 Rationale for this Study

Previous findings support the hypothesis of an overactive VAN in pediatric anxiety disorders and suggest that reducing VAN reactivity may have a specific effect in reducing anxiety symptoms. Yet, no treatments have been developed to explicitly correct VAN dysfunction by directly targeting this network. The treatment studied in this project aims to fill that gap. The rationale of this research is that it could lead to a novel, safe, mechanism-based treatment for a major public health problem.

C Study Objectives

C1 Primary Aim

Test the efficacy of a novel computer-based cognitive training program in the treatment of pediatric anxiety disorders using a pilot double-blind, randomized, placebo-controlled

design. The primary outcome will be reduction in symptoms of anxiety as measured by the Pediatric Rating Scale (PARS).

C2 Secondary Aim

Uncover the neural effects of the cognitive training program using functional magnetic resonance imaging (fMRI).

C3 Rationale for the Selection of Outcome Measures

The PARS is a clinician-administered measure of pediatric anxiety that incorporates both parent and child report.²⁶ Because it includes multiple informants and is anchored by a clinician, it has high reliability and validity and is widely used.

D Investigational Agent

D1 Preclinical Data

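### Carrying the last observation forward turns every missing Visit 11 PARS into zero change: a small loss at equal 10% dropout, larger only if dropout differs by arm

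*Combined protocol and SAP*

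**What the plan says.** G4 gives one missing-data rule for the whole trial: "We will use an intention-to-treat analysis and carry the last observation forward". It adds a follow-up comparison among completers.

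The PARS is given to parent and child at Visit 1 (F2); the child's part is to "participate in the child version of the K-SADS and PARS". The only other scheduled PARS is at Visit 11 (F5): "This visit will be after all 8 training sessions are completed and is identical to visit 1". Between them, F4 collects only the SCARED, at sessions 2, 4, 6 and 8, in the office or by e-mailed survey.

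For the PARS, G3 plans: "We will perform a 2 x 2 ANOVA with treatment arm (active versus sham) and time (pre- versus post-training) as effects of interest". For the SCARED it plans a mixed repeated-measures model on change from baseline.

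G3 is not consistent on which outcome is primary. It opens with "The primary outcome will be reduction in symptoms of anxiety as measured by the SCARED in study Phase 2" and adds "Secondary outcomes will include symptoms of anxiety on the PARS and diagnostic status". It then says "The primary outcome will be reduction in symptoms of anxiety as measured by the PARS", which agrees with C1.

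G1 gives an expected effect of 0.3 without a metric, 83% power, n = 90, and a 10% allowance for failure that is not split by arm.

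**The concern.** Where an outcome is measured once before and once after treatment, the last observation of a child who misses the second visit is the baseline. Carrying it forward records that the child did not change at all. This applies equally to a child who left after one session and to one who finished training but missed Visit 11.

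These zeros enter the analysis as if observed. If children in both arms tend to improve over the month, each zero pulls its arm's mean down. The estimated arm difference then depends partly on how many children are missing from each arm, and not only on what training did. The outcome affected is one that C1 and part of G3 call primary.

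For the SCARED the problem is milder. The carried value is usually a session score, and it is the baseline only for a child lost before session 2. Imputation is also unnecessary there, because the planned mixed model can use incomplete series directly.

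**Working it through.** **Inputs from the documents.** 90 children randomised 1:1, so 45 per arm (sections 2.d and I4); two-tailed comparison, effect 0.3, 10% failure, read here as dropout (G1); PARS at Visits 1 and 11 only (F2, F5).

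**Assumptions, because the documents give no figure.** Alpha 5%; SD of PARS change 1; dropout random within arm; improvement common to both arms c = 1.0, 0.5 or 0.3 SD; dropout by arm as shown.

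**The plan's own figure.** The stated 83% power does not reproduce with 0.3 read as an SD difference: a two-sided t-test with 45 per arm has 29% power. Read as Cohen's f, 0.3 is a difference of 2 x 0.3 = 0.6 SD and gives 80%. The metric is a separate question, so both 0.3 and 0.6 SD are used for the true difference D.

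**Formula.** The arm-by-time test in a 2 x 2 pre/post ANOVA is the two-sample t-test on change. Let pA and pS be the active and sham dropout. With dropouts set to zero change:

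- expected active mean = (1 - pA)(c + D)
- expected sham mean = (1 - pS)c
- bias in the difference = (1 - pA)(c + D) - (1 - pS)c - D = c(pS - pA) - pA·D

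Equal dropout p gives bias -p·D, so the estimate is (1 - p)D. The bias favours active training only if c(pS - pA) > pA·D, that is, if pS > pA(1 + D/c). It goes against active training when the inequality is reversed.

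**Example.** D = 0.6, c = 1.0, 15% active, 5% sham: bias = 1.0 x (0.05 - 0.15) - 0.15 x 0.6 = -0.10 - 0.09 = -0.19, so the estimate is 0.41.

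**Results.** Estimates are from the formula. Rejection rates are simulated with independent dropout for each child. Triplets are for c = 1.0 / 0.5 / 0.3.

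| True D | Dropout active/sham | Estimate, LOCF | Rejection, LOCF | Rejection, observed children |
|---|---|---|---|---|
| 0 | 10%/10% | 0 | 5.0% throughout | 5% |
| 0 | 5%/15% | 0.10 / 0.05 / 0.03 | 7.7% / 5.8% / 5.2% | 5% |
| 0 | 15%/5% | -0.10 / -0.05 / -0.03 | 7.8% at c = 1.0 (7.1% favouring sham) | 5% |
| 0.3 | 10%/10% | 0.27 | 24% / 26% / 26% | 27% |
| 0.3 | 15%/5% | 0.155 / 0.205 / 0.225 | 11% / 16% / 19% | 26% |
| 0.3 | 5%/15% | 0.385 / 0.335 / 0.315 | 44% / 37% / 34% | 27% |
| 0.6 | 10%/10% | 0.54 | 69% / 73% / 74% | 76% |
| 0.6 | 15%/5% | 0.41 / 0.46 / 0.48 | 45% / 59% / 64% | 76% |

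**Break-even.** With pA = 10% and D = 0.3, sham dropout must exceed 13%, 16% or 20% (c = 1.0, 0.5, 0.3) before the rule favours active training. With D = 0.6 it must exceed 16%, 22% or 30%.

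**Would SCARED-based imputation help?** A separate simulation took D = 0.6, a PARS-SCARED change correlation of 0.6, and SCARED change observed for dropouts. Dropout was 10% in both arms, 20%/5% or 5%/20%, either random or dependent on SCARED. Across these settings multiple imputation gave estimates of 0.59 to 0.61 with power of 74% to 77%. Carrying forward gave 0.33 to 0.72, and completers gave 0.49 to 0.71. The completers bias, about 0.10 SD in either direction, arose when dropout was unequal and depended on SCARED.

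**The case against.** The strongest reply is that the plan already contains the remedy for the case calculated above. If dropout is random within arm, the completers comparison in G4 is unbiased, and the last column of the table is that analysis. At equal 10% dropout, multiple imputation offers no power gain over it. This stands. The gain from SCARED-based imputation arises mainly when dropout depends on SCARED and differs by arm. It also needs a useful PARS-SCARED correlation and session SCARED scores from dropouts. A child lost before session 2 has only baseline SCARED.

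The design also gives reasons to expect similar retention. Children are blinded, both arms do the same task for the same number of trials, the course lasts four weeks, and completion is paid. Training staff are unblinded, so this is not proof, but nothing in the documents points to differential dropout.

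It can also be said that children who leave may be those who did not improve, so that zero change is near the truth. The bias would then be smaller. G4 does not offer this rationale.

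Four stronger readings are tempting and are not supported:

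- *The rule favours active training.* It does so only beyond the break-even. At 10%/15% with D = 0.3 the estimates are 0.320 / 0.295 / 0.285, so more sham dropout alone is not enough.
- *The rule is merely conservative.* With no effect and more active dropout it creates a false difference favouring sham.
- *Chance imbalance in dropout makes matters worse.* Each child drops out independently in the simulation, so the equal-dropout rows already average over such trials and still show 5% type I error.
- *The SCARED result is equally affected.* The effect on the planned time-by-treatment test was not calculated, and applying the rule to SCARED at all is one reading of an unrestricted sentence.

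**Conclusion.** The point holds as a method improvement. That a missing Visit 11 PARS becomes zero change follows directly from the visit schedule and G4.

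At the documented 10% attrition applied equally, the consequence is small: a 10% dilution of any true effect, no inflation of type I error, and a power loss against observed children of under 1 to about 7 points. It becomes moderate only under an assumed systematic difference in dropout between arms, and the largest distortions need a common improvement near 1 SD. At c = 0.3 with no effect, 5%/15% dropout gives only 0.03 SD and 5.2% rejection.

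A reader might infer that the trial's main result is unsafe. The documents do not support that. They give no dropout by arm, no SD and no expected sham improvement, and they plan a completers analysis that would show much of any distortion. If SCARED proves to be the primary outcome, the zero-change problem concerns a secondary outcome. The conflict over which outcome is primary is a separate issue.

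**What to change.** In G4, replace last observation carried forward:

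- Fit the SCARED mixed model to the observed session scores, without imputation.
- For a missing Visit 11 PARS, use multiple imputation or a joint likelihood model with arm, baseline PARS, and baseline and session SCARED. Keep every randomised child in the assigned arm, as G4 already intends.
- Keep the completers analysis as supportive, and report the number with missing Visit 11 PARS by arm.
- Optionally, add one delta-adjusted sensitivity analysis.

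Separately, reconcile the primary-outcome statements in C1 and G3, so that the missing-data rule attaches to a named outcome.

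The cost is a revision of the analysis text and a little more analysis work, with no new data collection. The replacement relies on data being missing at random given the variables in the model; the optional delta-adjusted analysis would test how much that matters.
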